ADAPTED COGNITIVE BEHAVIORAL THERAPY FOR DEPRESSION IN YOUTH WITH AUTISM

PROTOCOL

(CTL+click to jump to section)

CONTENTS

Adapted cognitive behavioral therapy for depression in youth with Autism -----	1
Research Components -----	1
Recruitment -----	2
Recruitment Resources -----	2
Maintaining Recruitment -----	2
Recruitment materials-----	2
INCLUSION/EXCLUSION CRITERIA -----	2
Scheduling Participants-----	6
Important Points to make -----	6
Visit Scheduling -----	7
Baseline Visit -----	7
Before Visit: Survey Kit -----	7
Setup & Consenting -----	8
Baseline Testing-----	9
Post-treatment Visit (Zoom) -----	9
Before Visit: Survey Kit -----	9
Post-treatment Testing (Zoom) -----	Error! Bookmark not defined.
Follow-up Visit (Zoom) -----	10
Before Visit: Survey Kit -----	10
Follow-up Testing (Zoom) -----	11

RESEARCH COMPONENTS

- **Baseline/Intake Visit**
 - Informed consent and assent
 - Baseline Assessments – research site offices (2-3 hours)
 - SRS-2 completed by parent
 - C-SSRS administered by clinician
 - ADOS-2 (if not administered in previous 24 months)
 - WASI-II (if not administered in previous 24 months)
- **Midpoint**
- **Post-treatment Visit**
- **Follow-up (12 weeks after post-treatment)**

RECRUITMENT

RECRUITMENT RESOURCES

- Vanderbilt University Medical Center, Department of Psychiatry and Behavioral Sciences, Outpatient Clinic
 - Flyers distributed to clinic groups at the Department of Psychiatry and Behavioral Sciences
 - Interested families will contact the PI ([name]) by email or phone to express interest in study.

MAINTAINING RECRUITMENT

- Maintain ongoing list of interested participants.

RECRUITMENT MATERIALS

- Study Flyers: Shared with adolescents and their parents upon enrolling in clinical groups at the Department of Psychiatry and Behavioral Sciences.

INCLUSION/EXCLUSION CRITERIA

Parent Inclusion Criteria

To be eligible to participate in this study, one must be at least 18 years of age and a parent or legal guardian of the adolescent participant with ASD. The parent must be able to provide current and historical observations of the functioning of the participant with ASD based on parent report. No data will be recorded from the medical record. The parent must live in close proximity to and have frequent contact with the participant with ASD. Additionally, the parent must complete several questionnaires about themselves (e.g., parenting stress, anxiety).

Parent Exclusion Criteria

Parents of adolescents with ASD who do not have frequent contact with the participant with ASD and/or unable to provide current and historical observations of the functioning of the participant with ASD may be excluded from the study.

Adolescent Inclusion Criteria

Clinical groups include male and female adolescents who are between 11-17 years of age at the time of study entry and who have been diagnosed with autism spectrum disorder (ASD). As part of the clinical service, this diagnosis will be confirmed by a clinical psychologist, pediatrician or psychiatrist with expertise in ASD and based on the DSM-V criteria (APA, 2013). Diagnosis may also be confirmed by elevated scores ($T > 59$) on the parent-rated Social Responsiveness Scale, Second Edition (SRS-2; Constantino, 2012) or the ADOS-2 (if not administered in previous 24 months). Adolescents will have average to above-average intellectual functioning in order to keep pace with the clinical groups, which will be assessed through clinician interview as part of the clinical process and/or may be confirmed by administration of the WASI-II (FSIQ > 69 ; if not administered in previous 24 months). Adolescents must be willing to attend study visits which include semi-structured interviews with the PI and questionnaires. No data will be recorded from the medical record.

Adolescent participants who assented to study participation when they were 17 years old will be asked to complete a study consent if they turn 18 years old during the course of the study.

Adolescent Exclusion Criteria

The following exclusion criteria only apply to participant's involvement in the research study. Meeting inclusion/exclusion criteria will not alter, preclude, nor interfere with the adolescent's participation in the clinical groups – this is a separate process.

- Youth with ASD and comorbid intellectual impairment will be excluded from the study, as the study protocol, assessments, and intervention are not designed for this population.
- Adolescents with severe medical conditions (e.g., uncontrolled seizures) and/or genetic disorders (e.g., Fragile X syndrome) will be excluded from the study.
- Participants whose diagnostic screening (i.e., SRS-2 total T-score > 59) does not confirm a diagnosis of ASD will not be eligible to continue the study.
- In order to maintain the safety all participants, youth with aggression toward others, self, or property in the past 6-months will be excluded from participation in the study. This information will be obtained during the initial phone screen with the parent and baseline visit.
- Adolescents who are unable to complete significant portions of the research protocol will be excluded.
- A participant must communicate using complete sentences and have fluent speech. If it appears that the participant does not understand some of the verbal or written information, the PI will use follow-up questions using simple language to ensure the participant understands the purpose and task demands of the study. After clarification, if the participant is unable to demonstrate understanding, respond to questions or willing to complete the questionnaires or protocols, the PI will determine if the participant should be excluded from the study.

If a participant evidences features of severe suicidality based on parental report (e.g., RCADS), self-report (e.g., RCADS), and/or clinical judgement (e.g., C-SSRS), it will immediately trigger a response. Specifically, the PI ([name]) will determine the best course of action (see full crisis plan below).

After enrollment in the study, if the participant endorses severe suicidal ideation (i.e., endorsing suicidality on the Revised Children's Anxiety and Depression Scale or severe suicidal ideation on the C-SSRS), the PI ([name]) will determine the best course of action. Options for addressing the concern may include contacting the participant's outpatient mental health care provider, prompt consultation with pediatric providers within the Department of Psychiatry and Behavioral Sciences, or referral for urgent psychiatric evaluation and treatment. If the threat is determined to not be imminent, the participant may stay enrolled within the study under careful observation. If determined necessary, the parent will be provided with local mental health resources. The PI will also inform the participant and parent of the importance of going to the Emergency Room should thoughts and feelings intensify. Finally, the participant will be notified that the Principal Investigator may withdraw the participant from the study due to suicidality in order for them to prioritize and receive the necessary care.

List of Mental Health Resources:

Vanderbilt University Medical Center (VUMC)

Vanderbilt Inpatient Hospitalization Program

[contact]

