Specialties: ADHD, Bipolar, Mood Disorders

Website: <https://www.childrenshospitalvanderbilt.org/doctors/[name]>

iPhone: [contact]

[name]. (Vanderbilt)

Specialties: Anxiety, Mood Disorders, Depression, Eating Disorders

Website: <https://www.childrenshospitalvanderbilt.org/doctors/[name]>

[contact]

24/7 Crisis Lines

Nashville - Centerstone Community Clinic: [contact]

Mental Health Cooperative Community Clinic: [contact]

National: [name]

Additional information about the screening procedures

The following questions will be asked of participants who endorse suicidal ideation. They are derived from the National Institute of Mental Health (NIMH) Ask Suicide Screening Questions.

<https://www.nimh.nih.gov/research/research-conducted-at-nimh/asq-toolkit-materials/asq-tool/asq-screening-tool.shtml>

1. In the past few weeks, have you wished you were dead? Yes No
2. In the past few weeks, have you felt that you or your family would be better off if you were dead? Yes No
3. In the past week, have you been having thoughts about killing yourself? Yes No
4. Have you ever tried to kill yourself? Yes No

If yes, how?

When?

If the patient answers yes to any of the above, ask the following question:

5. Are you having thoughts of killing yourself right now? Yes No

- If yes, please describe:
- Next steps: If patient answers "No" to all questions 1 through 4, screening is complete (not necessary to ask question #5). No intervention is necessary (*Note: Clinical judgment can always override a negative screen).
- If patient answers "Yes" to any of questions 1 through 4, or refuses to answer, they are considered a positive screen. Ask question #5 to assess acuity:
 - "Yes" to question #5 = acute positive screen (imminent risk identified)
 - Patient requires a STAT safety/full mental health evaluation. Patient cannot leave until evaluated for safety.
 - Keep patient in sight. Remove all dangerous objects from room. Alert physician or clinician responsible for patient's care.
 - "No" to question #5 = non-acute positive screen (potential risk identified)
 - Patient requires a brief suicide safety assessment to determine if a full mental health evaluation is needed. Patient cannot leave until evaluated for safety.
 - Alert physician or clinician responsible for patient's care.

SCHEDULING PARTICIPANTS

IMPORTANT POINTS TO MAKE

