- **Confirmation Email:** Send a confirmation email to the parent to confirm assessments.
- **Site Calendar:** Add Assessment to site Lab Calendar (Include subject ID, and who is doing the assessment)

BASELINE VISIT

BEFORE VISIT: SURVEY KIT

Send to parents before the baseline visit/have parents complete during visit:

- Cover Letter: instructions for questionnaire packet and appointment reminder
- Consent & Assent

- Tell parents to read, but not sign
 - Come with questions
 - We will review and sign at visit
- Parent-rated questionnaires about adolescent
 - SRS-2
 - RCADS – Parent version
 - QPQ – Parent version
 - EDI
 - ABAS-3
 - Demographic questionnaire
 - Service systems questionnaire
 - Medication questionnaire
 - Vanderbilt ADHD
 - DII
 - SPI Inventory
- Parent-rated questionnaires about self
 - PHQ-9/REMIT-5
 - GAD-7
 - Cohen Perceived Stress Scale
 - CD-RISC-10
 - PROMIS Global
 - PSI-4

(Parent Surveys: remind parents **not** to fill in child's name, DOB, and other identifying information)

SETUP & CONSENTING

- Arrive at the assessment facilities 30 minutes prior to family arrival time.
- Gather appropriate testing materials out of cabinets (C-SSRS, Depression Causes Inventory)
- When the family arrives bring them into a private family room and begin consenting. (15 minutes)
 - Ensure that 2 consent & 2 assent forms are signed by the family and research staff (1 copy for research team & 1 for family).
 - For any participants who are 17 years old, inform the parent and participant that the participant will have to repeat the consent process once they are 18 years old (i.e., transition to adult).
- After consenting and assenting, parent and child meet together with the study clinician to complete the semi-structured interview (C-SSRS; 15-20 minutes).
- After the interview...
 - Escort the parent to the family room where they'll wait until the assessment is done with child. Collect completed questionnaires from parent.
 - Leave the adolescent with the study clinician to complete assessments and questionnaires.
 - ADOS-2 may be administered (if not done in previous 24 months)
 - WASI-II may be administered (if not done in previous 24 months)
- **Review all questionnaires to confirm they are complete**
- At the end of visit, PI or study clinician will meet with both parent and adolescent to discuss study eligibility.

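### Parents complete the PHQ-9/REMIT-5 about themselves at three time points, but no visible step has it read for risk; if the form asks about self-harm, the protocol should say who reads it and when

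*Protocol*

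**What the plan says.** **Parents are enrolled.** Under Parent Inclusion Criteria the protocol sets an age and relationship requirement: "To be eligible to participate in this study, one must be at least 18 years of age and a parent or legal guardian". It adds that "the parent must complete several questionnaires about themselves".

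**The form.** PHQ-9/REMIT-5 appears among the questionnaires parents answer about themselves in the survey kits for baseline, post-treatment and follow-up. It is not in the midpoint list.

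**The suicidality rules.** These follow the bullets under Adolescent Exclusion Criteria. The first rule covers severe suicidality "based on parental report (e.g., RCADS), self-report (e.g., RCADS), and/or clinical judgement (e.g., C-SSRS"). The second applies after enrolment: "if the participant endorses severe suicidal ideation (i.e., endorsing suicidality on the Revised Children's Anxiety and Depression Scale", or severe ideation on the C-SSRS. Among the responses, "The PI will also inform the participant and parent of the importance of going to the Emergency Room" if things worsen. The resource list includes "24/7 Crisis Lines". The section on screening procedures opens with "The following questions will be asked of participants who endorse suicidal ideation".

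**Handling of parent forms.** At baseline (Setup & Consenting) the staff instruction is "Collect completed questionnaires from parent". Staff then check that every form has been filled in, and the PI or study clinician closes the visit by discussing eligibility with parent and adolescent. No form check is stated for post-treatment or follow-up.

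**The concern.** The protocol accepts that a questionnaire answer about suicidal thoughts calls for a prompt response, and it sets one out for the adolescent. The parent is also an enrolled person and answers a depression form about their own state, yet no comparable instruction is visible. If the form asks about thoughts of self-harm, the study would be collecting an answer that nobody is assigned to look at.

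What is at stake is the safety of enrolled adults and the study's ability to show that it acts on what it asks. The analysis would not prompt anyone to look either: the SAP covers attrition and adolescent depressive symptoms on the RCADS, and does not mention the parent form.

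**Working it through.** No figure in the plan bears on this, so the check is a trace of the text: where the form appears, what sets off a response, and who reads completed forms.

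**1. Where the form appears.** Baseline, post-treatment and follow-up: 3 of the 4 assessments, so up to 3 completed forms per parent.

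**2. Whether a suicidality rule reaches it.**
- The first rule gives its sources as examples (*e.g.*), so it is open as to instrument. It treats the parent's report as a source of information about the participant.
- The post-enrolment rule is introduced by *i.e.*, which limits it to the RCADS and the C-SSRS.
- The response text names participant and parent as separate people, offers consultation with pediatric providers, and gives the parent local resources as part of responding to the participant's ideation. Even the parent criteria attach the word participant to the adolescent.
- The screening questions come into play once ideation has been endorsed. They do not say how an endorsement on a parent form would be noticed.

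The natural reading is that these rules are for the youth. A wider reading is possible, but it still lacks a detection step.

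**3. Whether the crisis-plan notes settle the matter.** The visit lists attach a crisis-plan note to one form. Set against the other forms:

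| Form | Named in a suicidality rule | Listings | Listings with a note |
|---|---|---|---|
| Youth RCADS | Yes | 4 | 4 |
| Parent RCADS (about the youth) | Yes | 4 | 0 |
| C-SSRS (testing lists) | Yes | 4 | 0 |
| PHQ-9/REMIT-5 (parent about self) | No | 3 | 0 |

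Two forms that are named triggers carry no note at any listing. A missing note therefore does not show that a trigger is missing. The point rests on steps 2 and 4.

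**4. Whether anyone is told to read the parent form.**

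| Time point | Stated form check | Parent meets a clinician | Clinician told to read the form |
|---|---|---|---|
| Baseline | Yes, for completeness | Yes: joint interview and closing meeting | No |
| Post-treatment | None | Yes: joint interview | No |
| Follow-up | None | Yes: joint interview | No |

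A form check is stated at 1 of 3 time points, and a check for risk at 0 of 3. The joint interviews are described in the visit breakdown under Scheduling Participants and, for baseline, under Setup & Consenting.

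**5. Timing.** The baseline kit may be completed at the visit. The post-treatment and follow-up kits are headed as before-visit material. Follow-up forms go out about 10 weeks after post-treatment for a visit at 12 weeks, so dispatch precedes the visit by about 12 − 10 = 2 weeks. When forms come back is not stated, so no delay between an answer and a clinician seeing the parent can be calculated.

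**The case against.** The strongest objection is that the point depends on material nobody can see here. The documents do not print the items of the PHQ-9/REMIT-5, and the slash leaves open which items are used. Without a self-harm item, all that remains is that a parent mood form is not named in a suicide rule, which is no defect. This stands in full and makes the point conditional.

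Second, part of the resource list inside the suicidality procedure was not available, nor were the consent pages, which are a natural place to deal with a parent's own disclosures. This also stands. The claim can only be that no visible step exists.

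Third, the open wording might cover parents: the first rule gives examples only, the screening questions are for participants who endorse ideation, and the crisis lines carry no age limit. This stands in part. A reader might infer that the plan offers a distressed parent nothing, and the documents do not support that. But a response that starts once ideation is known does not make anyone read the form.

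Fourth, parents see a clinician at every time point where they complete the form. That is correct and narrows the gap. A reader might suppose that parents have no clinician contact after baseline; the visit breakdown says otherwise. What remains is that the interview is not linked to the form.

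Fifth, the post-enrolment rule is sound for its purpose. It defines a trigger for adolescents, and leaving out an adult form is not an error in it. Agreed: what is lacking is a companion rule for the parent.

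**Conclusion.** The point holds in a limited, conditional form. Enrolled parents complete the PHQ-9/REMIT-5 at three time points, the visible suicidality rules are written for the youth, and no visible step has the parent form read for risk. Clinician contact at all three time points reduces the gap without closing it.

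It rests on two assumptions: that the form in use includes a self-harm item, and that the unavailable text does not already provide for parent disclosures. If either fails, nothing needs to change.

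Two stronger inferences should be resisted. The contrast between 4 of 4 noted youth RCADS listings and 0 of 3 noted parent listings might look like proof of an omission. It is not, because the parent RCADS and the C-SSRS are named triggers with no notes. Nor do the documents support any statement about how many parents would be affected or how long an answer would wait.

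The trial's estimates and analysis are unaffected. This is a cheap improvement to participant safety, held with medium confidence.

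**What to change.** First confirm whether the parent form contains a self-harm item. If it does:

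- In the suicidality procedure, add that a parent's endorsement of that item leads to PI review, using the screening questions and crisis lines already in the protocol, with an adult referral option if the full resource list lacks one.
- In the three survey-kit lists, state beside PHQ-9/REMIT-5 that the item is read on receipt. At post-treatment and follow-up this should be no later than the start of the joint clinician interview. At baseline the plan collects forms after that interview, so either collect the form earlier or read it before the closing meeting with the family.

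Alternatively, use a parent form without the item.

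The cost is a sentence in one section and a line in three lists, a brief look at up to three forms per parent, and occasional PI follow-up with a parent. No new instrument, staff or scheduled visit is needed.

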Specialties: ADHD, Bipolar, Mood Disorders

Website: <https://www.childrenshospitalvanderbilt.org/doctors/[name]>

iPhone: [contact]

[name]. (Vanderbilt)

Specialties: Anxiety, Mood Disorders, Depression, Eating Disorders

Website: <https://www.childrenshospitalvanderbilt.org/doctors/[name]>

[contact]

24/7 Crisis Lines

Nashville - Centerstone Community Clinic: [contact]

Mental Health Cooperative Community Clinic: [contact]

National: [name]

Additional information about the screening procedures

The following questions will be asked of participants who endorse suicidal ideation. They are derived from the National Institute of Mental Health (NIMH) Ask Suicide Screening Questions.

<https://www.nimh.nih.gov/research/research-conducted-at-nimh/asq-toolkit-materials/asq-tool/asq-screening-tool.shtml>

1. In the past few weeks, have you wished you were dead? Yes No
2. In the past few weeks, have you felt that you or your family would be better off if you were dead? Yes No
3. In the past week, have you been having thoughts about killing yourself? Yes No
4. Have you ever tried to kill yourself? Yes No

If yes, how?

When?

If the patient answers yes to any of the above, ask the following question:

5. Are you having thoughts of killing yourself right now? Yes No

- If yes, please describe:
- Next steps: If patient answers "No" to all questions 1 through 4, screening is complete (not necessary to ask question #5). No intervention is necessary (*Note: Clinical judgment can always override a negative screen).
- If patient answers "Yes" to any of questions 1 through 4, or refuses to answer, they are considered a positive screen. Ask question #5 to assess acuity:
 - "Yes" to question #5 = acute positive screen (imminent risk identified)
 - Patient requires a STAT safety/full mental health evaluation. Patient cannot leave until evaluated for safety.
 - Keep patient in sight. Remove all dangerous objects from room. Alert physician or clinician responsible for patient's care.
 - "No" to question #5 = non-acute positive screen (potential risk identified)
 - Patient requires a brief suicide safety assessment to determine if a full mental health evaluation is needed. Patient cannot leave until evaluated for safety.
 - Alert physician or clinician responsible for patient's care.

SCHEDULING PARTICIPANTS

IMPORTANT POINTS TO MAKE

- Studying the effects of an adapted Cognitive Behavioral Therapy (CBT) for adolescents with autism and depressive symptoms. Participants are recruited from ongoing clinical group treatments at the Department of Psychiatry and Behavioral Sciences.
- 4 assessment periods: baseline, midpoint, post-treatment, and follow-up (12 weeks after post-treatment).
- Autism
- Ages 11-17
- Does your child use complete sentences to communicate? How are your child's language skills—must have fluent speech/speak in complete sentences.

- Visit breakdown
 - **Intake/Baseline** (up to 2 hours with breaks)
 - Diagnostic confirmation (ADOS, ask if completed within last 2 years)
 - General cognitive abilities (ask if diagnosis of intellectual disability and WASI-II, ask if completed within last 2 years)
 - Parents and adolescents together will complete a brief, semi-structured interview with a clinician
 - Adolescents will complete questionnaires.
 - Parents will complete questionnaires that ask about their adolescent, and several questionnaires that ask about their own experiences as parents.
 - **Midpoint** (6 weeks into groups): Youth and parent questionnaires and clinical interview (up to 1 hour).
 - **Post-treatment** (after 12 weeks of clinical groups; up to 2 hours with breaks)
 - Parents and adolescents together will complete the same semi-structured interview with a clinician.
 - Adolescents will complete the same questionnaires.
 - Parents will complete the same questionnaires that ask about their adolescent, and several questionnaires that ask about their own experiences as parents.
 - **Follow-up** (12 weeks after post-treatment; up to 2 hours with breaks)
 - Parents and adolescents together will complete the same semi-structured interview with a clinician.
 - Adolescents will complete the same questionnaires.
 - Parents will complete the same questionnaires that ask about their adolescent, and several questionnaires that ask about their own experiences as parents.

Study Timeline: Phonescreen...if eligible... → Baseline Visit → Participation in clinical groups for 12 weeks (Midpoint week 6) → Post-treatment Visit → Follow-up Visit (12 weeks after post-treatment)

VISIT SCHEDULING

General Notes:

- Add each component to Lab Calendar.
- Invite [name] and all other involved lab members to all scheduled calendar components.
- Give reminder call/email to family several days before event.

Assessments

- **Establish Days/Times** for when assessments can be scheduled.
- **Confirmation Email:** Send a confirmation email to the parent to confirm assessments.
- **Site Calendar:** Add Assessment to site Lab Calendar (Include subject ID, and who is doing the assessment)

BASELINE VISIT

BEFORE VISIT: SURVEY KIT

Send to parents before the baseline visit/have parents complete during visit:

- Cover Letter: instructions for questionnaire packet and appointment reminder
- Consent & Assent

- Tell parents to read, but not sign
 - Come with questions
 - We will review and sign at visit
- Parent-rated questionnaires about adolescent
 - SRS-2
 - RCADS – Parent version
 - QPQ – Parent version
 - EDI
 - ABAS-3
 - Demographic questionnaire
 - Service systems questionnaire
 - Medication questionnaire
 - Vanderbilt ADHD
 - DII
 - SPI Inventory
- Parent-rated questionnaires about self
 - PHQ-9/REMIT-5
 - GAD-7
 - Cohen Perceived Stress Scale
 - CD-RISC-10
 - PROMIS Global
 - PSI-4

(Parent Surveys: remind parents **not** to fill in child's name, DOB, and other identifying information)

SETUP & CONSENTING

- Arrive at the assessment facilities 30 minutes prior to family arrival time.
- Gather appropriate testing materials out of cabinets (C-SSRS, Depression Causes Inventory)
- When the family arrives bring them into a private family room and begin consenting. (15 minutes)
 - Ensure that 2 consent & 2 assent forms are signed by the family and research staff (1 copy for research team & 1 for family).
 - For any participants who are 17 years old, inform the parent and participant that the participant will have to repeat the consent process once they are 18 years old (i.e., transition to adult).
- After consenting and assenting, parent and child meet together with the study clinician to complete the semi-structured interview (C-SSRS; 15-20 minutes).
- After the interview...
 - Escort the parent to the family room where they'll wait until the assessment is done with child. Collect completed questionnaires from parent.
 - Leave the adolescent with the study clinician to complete assessments and questionnaires.
 - ADOS-2 may be administered (if not done in previous 24 months)
 - WASI-II may be administered (if not done in previous 24 months)
- **Review all questionnaires to confirm they are complete**
- At the end of visit, PI or study clinician will meet with both parent and adolescent to discuss study eligibility.

- If family is eligible, make note of this in research folder and general dates/times that family is available for remaining visits.
- If family is not eligible, make note of this in research folder; no subsequent research visits scheduled.

BASELINE TESTING

TASKS

- **The following administration of tests and timelines are normative, but can vary from child to child**
 - Columbia Suicide Severity Rating Scale – 15-20 minutes
 - RCADS Self-Report —5-7 minutes (If the child endorses item #35 suggesting suicidal ideation, the crisis plan implemented in the Inclusion\Exclusion Criteria section).
 - QPQ Self Report – 5 minutes
 - Cohen's Perceived Stress - 5 minutes
 - Rosenberg – 3 minutes
 - LEAP – 3 minutes
 - ADOS-2 – 30-45 minutes (if not administered in previous 24 months)
 - WASI-II – 30-45 minutes (if not administered in previous 24 months)
 - CATI – 10-11 minutes
 - DII – 4-5 minutes
 - BFNE – 2-3 minutes
 - SCS-SF – 6-7 minutes
 - PROMIS Global – 2-3 minutes

MIDPOINT

TASKS

- **Youth questionnaires**
 - Columbia Suicide Severity Rating Scale – 15-20 minutes
 - RCADS Self-Report —5 minutes (If the child endorses item #35 suggesting suicidal ideation, the crisis plan implemented in the Inclusion\Exclusion Criteria section).
 - QPQ Self Report – 5 minutes
- **Parent questionnaires**
 - RCADS – Parent version
 - QPQ – Parent version
 - EDI

POST-TREATMENT

BEFORE VISIT: SURVEY KIT

- Parent-rated questionnaires about adolescent
 - SRS-2
 - RCADS – Parent version

- QPQ – Parent version
- EDI
- Treatment Satisfaction Survey, Parent Version
- DII
- Parent-rated questionnaires about self
 - PHQ-9/REMIT-5
 - GAD-7
 - Cohen Perceived Stress Scale
 - CD-RISC-10
 - PROMIS Global
 - PSI-4

(Parent Surveys: remind parents **not** to fill in child's name, DOB, and other identifying information)

TASKS

- **The following administration of tests and timelines are normative, but can vary from child to child**
 - Columbia Suicide Severity Rating Scale – 15-20 minutes
 - RCADS Self-Report —5 minutes (If the child endorses item #35 suggesting suicidal ideation, the crisis plan implemented in the Inclusion\Exclusion Criteria section).
 - QPQ Self Report – 5 minutes
 - Cohen's Perceived Stress - 5 minutes
 - Rosenberg – 3 minutes
 - LEAP – 3 minutes
 - Treatment Satisfaction Survey, Teen Version – 3 minutes
 - CATI – 10-11 minutes
 - DII – 4-5 minutes
 - BFNE – 2-3 minutes
 - SCS-SF – 6-7 minutes
 - PROMIS Global – 2-3 minutes

FOLLOW-UP VISIT

BEFORE VISIT: SURVEY KIT

- Parent-rated questionnaires about adolescent
 - SRS-2
 - RCADS – Parent version
 - QPQ – Parent version
 - EDI
 - DII
- Parent-rated questionnaires about self
 - PHQ-9/REMIT-5
 - GAD-7
 - Cohen Perceived Stress Scale

- CD-RISC-10
- PROMIS Global
- PSI-4

(Parent Surveys: remind parents **not** to fill in child's name, DOB, and other identifying information)

FOLLOW-UP TESTING

TASKS

- **The following administration of tests and timelines are normative, but can vary from child to child**
 - Columbia Suicide Severity Rating Scale – 15-20 minutes
 - RCADS Self-Report - 5 minutes (If the child endorses item #35 suggesting suicidal ideation, the crisis plan implemented in the Inclusion\Exclusion Criteria section).
 - QPQ Self Report – 5 minutes
 - Cohen's Perceived Stress - 5 minutes
 - Rosenberg – 3 minutes
 - LEAP – 3 minutes
 - CATI – 10-11 minutes
 - DII – 4-5 minutes
 - BFNE – 2-3 minutes
 - SCS-SF – 6-7 minutes
 - PROMIS Global – 2-3 minutes

All forms must be completed by same rater in assessments (i.e. same parent/guardian)!

